#### 8.3 Potential Benefits

The potential direct benefits to subject participation in this study is enhanced pain control, opioid reduction, closer follow-up for depression symptoms, and reduced depression risk. There are societal benefits in that there will be increased knowledge about the use of ketamine after birth to reduce depression, alleviate pain and decrease opioid use. Ultimately, the results of this study, if significant, will enable health care providers to improve the health of mothers.

### 9 Protection Against Risks

# 9.1 Management of drug related toxicity

The PI is a practicing, board-certified clinical anesthesiologist with extensive experience in the administration of this study drug under normal clinical circumstances. The study drug will be started during routine anesthesia care where monitoring is the strictest and closest, thereby enabling early detection of any safety events. The patients will remain monitored in an appropriate care environment throughout the duration of the 12-hour drug infusion, enabling timely detection and treatment of any serious events should they occur. Staff will also be trained to be familiar with common and uncommon side/adverse events for reporting.

Supportive care drugs that may be used in the event of drug related toxicity:

- Event: Persisting unresolved hemodynamic side effects defined as Systolic blood pressure <80 or >160, heart rate <40 or >120, unresolved after 3 consecutive measurements within a 15-minute interval
  - Supportive care medications:
  - Labetalol 10-20mg IVP or Hydralazine 10-25mg IVP p.r.n. hypertension at discretion of managing anesthesiologist.
- Event: Persisting side effects sedation, dizziness, lightheadedness, bad dreams, hallucinations, or other side effects that are reported as not acceptable to patient or clinicians, despite minimizing infusion rate
  - Supportive care medications:
  - o Midazolam 1-4mg IVP p.r.n. dysphoria, at discretion of managing anesthesiologist.

Refer to Section 6.8 for Rescue Drugs.

Refer to Section 6.3 of the protocol for instructions on dose delays and modifications.

# 9.2 Management of research related risks

All research interventions/activities will be conducted in private patient care areas. The collection of sensitive information about subjects is limited to the amount necessary to achieve the aims of the research, so that no unneeded sensitive information is collected.

All demographic and clinical information about the subject will be stored in an electronic password-guarded study database under the supervision of the Investigator for this protocol. The electronic system REDCap has features that can enable its use as certifiably compliant with the DFTA regulations at 21 CFR part 11 but due to the limited scope of this clinical research study, the electronic data recording system has not been certified as fully compliant. The data will be stripped of individual identifiers at the time of analysis and stored anonymously with a subject number. Information linking subject identifiers with the coded subject number will be stored under password proection on computers in locked areas, with access to the database manager. Access to the database will be limited to the data manager and staff under the supervision of the Investigator.

All staff involved in this study are properly credentialed and instructed in the areas of testing, confidentiality, and safety. All study team members will be properly trained on protocol requirements, trained in HIPAA/privacy procedures, and GCPs. Research procedures performed for study purposes will be performed by qualified individuals as evidenced by education, experience, and/or training. All members of the study team will have the required human subjects and confidentiality training, which includes information about maintaining data integrity and security. Confidentiality will be guarded using established procedures such as storing data in locked cabinets within locked offices or locked data rooms, coding CRFs and research specimens by study identification numbers rather than any personal identifying information to avoid revealing the identity of subjects, and aggregating data across participants. The key linking names and study identification numbers will be kept separately from the data sets with limited access by study personnel. Only study personnel will have access to the data sets on protected servers.

The Investigator will retain the data for the entire period of this study and will retain the specified records and reports for up to seven years after the study's publication. The Investigator may continue to use and disclose subjects' de-identified information for the purpose of this study for a minimum of seven years after final reporting or publication of the study. If the subject and/or legal representative decide to withdraw or be withdrawn from study participation, they may request in writing that the study data and samples be destroyed. Subject names or other directly identifiable information will not appear on any reports, publications, or other disclosures of clinical study outcomes.

Clinical data recorded on the electronic database will include intraoperative obstetrician case report forms completed by the obstetrician at the end of surgery, and hospital postpartum morphine equivalent dosing.

#### 10 Adverse Events and Serious Adverse Events

The proposed clinical trial will use the FDA definition of an adverse event (AE). Adverse event means any untoward medical occurrence associated with the use of a drug in humans, whether considered drug related.

The proposed clinical trial will use the FDA definition of SAE. A serious adverse event is any untoward clinical event that is thought by either the investigator or the sponsor to be *unexpected and at least possibly related* to the study and results in any of the following:

- 1. Death
- 2. A life-threatening adverse event
- 3. Inpatient hospitalization or prolongation of an existing hospitalization
- 4. A persistent or significant incapacity or substantial disruption of the ability to conduct normal life functions
- 5. A congenital anomaly or birth defect
- 6. Important medical events that may not result in death, be life threatening, or require hospitalization may be considered serious when, based upon appropriate medical judgment, they may jeopardize the patient, or subject, and may require medical, or surgical intervention to prevent one of the serious outcomes listed above.

Adverse events will be assessed on each participant at stated intervals in Figure 2 section 1.1, both during infusion, and for 12 hours after infusion discontinuation. Duration of monitoring is based on known pharmacokinetics of ketamine.

When an adverse event is discovered, the event will be assessed for severity, relatedness, and expectedness. All adverse events will be documented in the research records and followed until resolved or back to baseline grade.

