#### 8 Potential Risks and Benefits

# 8.1 Reasonably Foreseeable Risks Related to Study Drug

Common side effects of ketamine are sedation, dizziness, lightheadedness, bad dreams, hallucinations, euphoria, dysphoria, nausea, vomiting. These risks are minimized by using doses below the doses that we typically see these side effects. Seriousness: mild to moderate.

Uncommon effects of ketamine include hypertension or hypotension, tachycardia, or bradycardia. These risks are minimized as much as possible by using doses below the doses that we typically see these effects. If these effects are noted, the drug will be stopped until the effects dissipate. Should the effects not dissipate, the PI will evaluate and determine whether the patient requires additional care. If these uncommon effects are experienced, an SAE log will be completed and the IDSMB and IRB notified. Seriousness: mild to moderate

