#### 10.3 Expectedness

The Principal Investigator will be responsible for determining whether an AE is expected or unexpected. An AE will be considered unexpected if the nature, severity, or frequency of the event is not consistent with the information previously described (sections 8.2 and 9.1). Note that the risks listed in Section 8.1 are considered expected and would not require reporting *unless* the frequency or severity is greater than expected. Events not listed in Section 8.1 but that are listed in the FDA-approved package insert, should

also be considered expected. In such cases, depending on the nature and severity of the event, an amendment may be necessary to add the risk to Section 8.1 and the consent form document.

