# 10.4 Reporting Serious Adverse Events

If there is a suggestion that any research procedures have resulted in an injury to subjects, there will be immediate contact with the Principal Investigator who is listed on the first page of the informed consent documents. Any SAE, which is determined by the PI to be unexpected and at least possibly related to study intervention, will be reported to the IRB as soon as possible. The PI is responsible for notifying the FDA within required timeframes. The IDSMB will be notified in writing at the soonest possible timepoint that the event has been identified. The IRB and FDA and will include all known details regarding the nature of the SAE. Outcomes of SAEs not previously reported will be reported to the PI, IRB and FDA via a follow-up report.

Life-threatening or fatal unexpected adverse events associated with the use of the study drug or procedures must be reported to the IRB within 24 hours of discovery of the incident with subsequent follow-up submission of a detailed written report. The IDSMB and IRB will be notified by telephone or facsimile transmission of a human adverse event that is fatal or life-threatening no later than 7 calendar days after receiving the respective human adverse event information, followed by the subsequent submission of a written IND Safety Report. Serious and unexpected adverse events associated with the use of the study drug or procedures will be reported to the IRB with subsequent follow-up submission of a detailed written report in accordance with the respective policies and procedures of the IRB. A summary report of the findings will be prepared and submitted to the regulatory agencies. A written IND Safety Report (i.e., Form FDA 3500A) will be submitted to the FDA as soon as possible and, in no event, later than 15 calendar days following the investigator-sponsor's receipt of the respective adverse event information.

A summary of the SAEs that occurred during the previous year will be included in the FDA annual progress report as well as in the annual IRB continuing review.

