#### 11.1 Adverse Events Requiring Discontinuation

For this study, a serious adverse event is any untoward clinical event that is thought by either the investigator or the sponsor to be related to the study and results in any of the following outcomes:

- 1. Death
- 2. A life-threatening adverse event
- 3. Inpatient hospitalization or prolongation of an existing hospitalization

- 4. A persistent or significant incapacity or substantial disruption of the ability to conduct normal life functions.
- 5. A congenital anomaly or birth defect
- 6. Important medical events that may not result in death, be life threatening, or require hospitalization may be considered serious when, based upon appropriate medical judgment, they may jeopardize the patient, or subject, and may require medical, or surgical intervention to prevent one of the serious outcomes listed above.

If clinically important and unexpected adverse experiences or clinically important study-related adverse experiences occur, they will be recorded on the adverse event case report form.

Adverse Events Reporting Timeline is documented in 10.4.

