# 12.3 Analysis of Primary Endpoint

Maximum Tolerated (Ketamine) Dose (MTD): The MTD will be defined as the dose at which fewer than 33% of patients experience intolerable effects.

Tolerability (dichotomous Yes/No)

- Tolerability (YES) will be defined as: lack of serious adverse events (serious adverse event defined as: severe unresolved hemodynamic effect: systolic blood pressure <80 or >160, heart rate <40 or >120).
- *Lack of Tolerability* will be defined as presence of any serious adverse event (i.e., severe unresolved hemodynamic effect: systolic blood pressure <80 or >160, heart rate <40 or >120).

For this MTD study, rates of the primary endpoint will be reported as numbers and percentages. Rates of blood pressure and heart rate events will be reported as numbers and percentages.

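### Section 10 makes unexpectedness and relatedness conditions of an SAE and three other sections use the term differently, so serious events judged expected or unrelated can be missing from SAE counts and the annual SAE summary

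*Combined protocol and SAP*

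**What the plan says.** All references are to the combined protocol and SAP.

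- **Section 10** states "The proposed clinical trial will use the FDA definition of SAE". It then requires that the event be thought, by the investigator or the sponsor, "to be *unexpected and at least possibly related* to the study" before any of six listed outcomes makes it serious. The section closes by saying that each adverse event is assessed for severity, relatedness and expectedness, and that all adverse events are documented and followed.
- **Section 11.1** repeats the six outcomes, but the event need only be thought "to be related to the study and results in any of the following outcomes". Unexpectedness is not mentioned.
- **Section 12.3**, in defining tolerability, has "serious adverse event defined as: severe unresolved hemodynamic effect", with systolic pressure and heart rate limits. Section 3.4.1 uses the same limits and calls the event an adverse event.
- **Section 8.1** covers hypertension, hypotension, tachycardia and bradycardia. It rates them mild to moderate and says that, if they occur, "an SAE log will be completed and the IDSMB and IRB notified".
- **Section 10.3** says "the risks listed in Section 8.1 are considered expected" and need no reporting unless their frequency or severity exceeds expectation. Events in the package insert but not in Section 8.1 are also to be treated as expected.
- **Section 10.4** sends to the IRB any SAE "which is determined by the PI to be unexpected and at least possibly related to study intervention". It also provides for a yearly SAE summary in the FDA progress report and the IRB continuing review.

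**The concern.** Seriousness, relatedness and expectedness are three separate attributes of an event. Seriousness describes what happened to the patient, and the other two describe how the event is attributed and whether it was foreseen. When all three are folded into one definition, a patient can have one of the six outcomes and still have no SAE on record, because someone judged the event to be foreseen or caused by something else.

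That matters here because the trial exists to describe tolerability in a small open-label cohort. Many of the effects of interest are listed in advance as ketamine risks. Attribution is also hard: the infusion starts shortly after cesarean delivery under spinal anesthesia, with intrathecal opioids and vasopressors also given (Section 7, Intraoperative Procedures). At stake is whether the SAE count and the yearly SAE summary mean the same thing to everyone who reads them.

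**Working it through.** The documents give no figure to reproduce and no arithmetic applies. The check sets the uses of the term side by side, follows three kinds of event through them, and then asks which outputs depend on the label.

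**1. Conditions for the SAE label or SAE log, by section**

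| Section | One of six outcomes | Related | Unexpected | Other condition |
|---|---|---|---|---|
| 10 | required | required (at least possibly) | required | none |
| 11.1 | required | required | not required | none |
| 12.3 | not required | not required | not required | severe unresolved vital-sign excursion |
| 8.1 (SAE log) | not required | not stated | not required; listed effects are expected under 10.3 | hypertension, hypotension, tachycardia or bradycardia |

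No two rows agree.

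**2. Section 10 against its own subsections**

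- Section 10 says that relatedness and expectedness are assessed once an event has been found. That treats them as separate attributes.
- Section 10.2 grades SAEs on a relatedness scale that runs down to a not-related grade. Under the Section 10 definition no SAE could receive that grade.
- Section 10.4 selects from the SAEs those judged unexpected and at least possibly related. If the definition already contained both conditions, the selection would do nothing.

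So Sections 10.2 and 10.4 read naturally only if an SAE is defined by outcome. This follows from the protocol's own text, without consulting the regulation.

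**3. Three events traced**

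| Event | Section 10 | Section 11.1 | Section 12.3 | Section 8.1 log |
|---|---|---|---|---|
| A. One of the six outcomes; related; judged expected | not an SAE | SAE | SAE only if it is the hemodynamic event | only if a listed hemodynamic effect |
| B. One of the six outcomes; judged unrelated | not an SAE | not an SAE | as for A | as for A |
| C. Persisting systolic pressure above 160; none of the six outcomes | not an SAE | not an SAE | SAE | logged and notified, yet under 10.3 not reportable unless worse or more frequent than expected |

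Events A and B can lose the label. Event C can gain it with no serious outcome. For C, Sections 8.1 and 10.3 also give opposite instructions on notification.

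**4. Which outputs depend on the label**

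- Dependent: any count of SAEs, and the yearly SAE summary to FDA and IRB (Section 10.4).
- Not changed by the definition: the SAE report to the IRB that Section 10.4 limits to unexpected and related events, since it applies those two conditions itself.
- Independent: documentation and follow-up of all AEs (Section 10); the AE case report form for clinically important study-related events (Section 11.1); routing of AEs and SAEs through an investigator to the IDSMB and IRB (Section 13); DSMB review of events behind withdrawals, whose triggers carry no expectedness or relatedness condition (Section 11.1, Withdrawal of Subjects due to Adverse Events); the DLT criteria (Section 3.4.1); and the blood pressure and heart rate event rates (Section 12.3).

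**The case against.** The strongest reply is that little is lost in practice. Every AE is documented and followed, AEs as well as SAEs go to the IDSMB and IRB, and an event that prolongs hospitalization triggers withdrawal and so DSMB review, whatever its expectedness. All of that stands. A reader might infer from Section 10 that serious but expected events vanish from the safety record, or that the DSMB would undercount toxicity. The documents do not support either reading. The yearly SAE summary is addressed to FDA and IRB and is not named as the DSMB's source.

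A second reply concerns severe hypertension. Section 8.1 rates its listed effects mild to moderate, and Section 10.3 makes an event unexpected when its severity exceeds what was described. A life-threatening form could then qualify as unexpected and, if possibly related, as an SAE under Section 10. This narrows the gap for event A but does not close it:

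- The call is a judgment by the PI in an open-label study.
- Section 10.3 compares the event with Sections 8.2 and 9.1, and Section 9.1 already describes persisting, unresolved hemodynamic effects.
- The package-insert sentence carries no severity qualifier, and the insert's contents are not in the documents.
- The sixth outcome, important medical events, turns on jeopardy and the need for intervention rather than on a severity grade.

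The reply does nothing for event B. A serious event judged unrelated fails both Section 10 and Section 11.1, however severe it is.

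**Conclusion.** The point holds as a defect in the SAE definition and in its use across Sections 8.1, 10, 11.1 and 12.3. Followed as written, Section 10 takes the SAE label from two classes of serious event: those judged expected, including through the package-insert clause, and those judged unrelated. SAE counts and the annual SAE summary can understate both, while Section 12.3 attaches the label to events that need not have any serious outcome.

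The effect cannot be quantified. A reader might note that one patient in a cohort of at most 12 is 1/12 = 8.3% and take that as the bias in an SAE rate. That is the weight of any single patient, not an estimate, and no SAE rate is a planned endpoint. A reader might also infer that the maximum tolerated dose (MTD) is affected. It is not affected by Section 10, because escalation rests on the DLT criteria in Section 3.4.1, and Section 12.3 gives its own meaning to the term it borrows.

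The conclusion assumes that Section 10 governs when SAEs are counted and summarized. If staff used Section 11.1 instead, only the events judged unrelated would be lost. The documents do not say which section prevails. The correction is worth making because the rule is wrong as written and cheap to put right.

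**What to change.** 1. In Sections 10 and 11.1, define an SAE by the six outcomes alone, in identical words.
2. Keep relatedness (Section 10.2) and expectedness (Section 10.3) as separate recorded fields, used only as the expedited-reporting filter in Section 10.4.
3. State that all SAEs are tabulated, and included in the annual summary, regardless of relatedness or expectedness; the two fields can be shown as columns.
4. In Section 12.3, replace the term serious adverse event with the term used in Section 3.4.1 for the same hemodynamic event.
5. Reconcile Section 8.1 with Section 10.3 on which listed effects are logged, in which log, and who is notified.

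The cost is wording changes and possibly a few more SAE entries. No dose, vital-sign limit, DLT criterion or sample size changes.

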#### 10.1 Severity

The severity of adverse changes in physical signs or symptoms will be classified as follows:

- *Grade 1 (Mild):* asymptomatic or mild symptoms; clinical or diagnostic observation only; intervention not indicated.
  - e.g., sedation, dizziness, lightheadedness, bad dreams, hallucinations, euphoria, dysphoria, nausea, vomiting
- *Grade 2 (Moderate):* minimal, local, or noninvasive intervention indicated; limiting ageappropriate ADL.
  - o e.g., dysphoria, vomiting
- *Grade 3 (Severe):* medically significant but not immediately life-threatening; hospitalization or prolongation of hospitalization indicated; disabling; limiting self-care/ADL.
  - o e.g., hypertensive urgency or emergency requiring escalated or inpatient treatment
- *Grade 4 (Life-threatening):* consequences; urgent intervention indicated.
  - o e.g., stroke from uncorrected severe hypertension

• *Grade 5 (Death):* event is a direct cause of death.

An independent DSMB will define frequency of monitoring of the tolerability and DLT data.

#### 10.2 Relatedness

Adverse Events and Serious Adverse Events will be subject to the following criteria to determine the relatedness of the experienced event to the research study, protocol, and/or drug.

- Definitely Related There is clear evidence to suggest a causal relationship, and other possible
  contributing factors can be ruled out. The clinical event occurs in a plausible time relationship to
  study intervention administration and cannot be explained by concurrent disease or other drugs or
  chemicals. The response to withdrawal of the drug is clinically plausible. The event must be
  pharmacologically or phenomenologically definitive.
- Probably Related There is evidence to suggest a causal relationship, and the influence of other
  factors is unlikely. The clinical event occurs within a reasonable time after administration of the
  study intervention, is unlikely to be attributed to concurrent disease or other drugs or chemicals
  and follows a clinically reasonable response on withdrawal of the study drug.
- Possibly Related There is some evidence to suggest a causal relationship (e.g., the event occurred within a reasonable time after administration of the study medication). However, other factors may have contributed to the event (e.g., the participant's clinical condition, other concomitant events). Although an AE may rate only as "possibly related" soon after discovery, it can be flagged as requiring more information and later be upgraded to "probably related" or "definitely related", as appropriate.
- Unlikely to be related A clinical event whose temporal relationship to study intervention
  administration makes a causal relationship improbable (e.g., the event did not occur within a
  reasonable time after administration of the study intervention) and in which other drugs or
  chemicals or underlying disease provides plausible explanations (e.g., the participant's clinical
  condition, other concomitant treatments).
- Not Related The AE is completely independent of study intervention administration, and/or evidence exists that the event is related to another etiology. There will be an alternative, definitive etiology documented by the clinician.

